6.1 Risk assessment

This study has been categorised as a Low Risk, where the level of risk is no higher than the risk of standard medical care.

7 Site and Investigator selection

This study will be carried out at three centres: Cardiff and Vale University Health Board, Churchill Hospital, Oxford and Queen Elizabeth Hospital, Birmingham.

8 Participant selection

Participants are eligible for the study if they meet all of the following inclusion criteria and none of the exclusion criteria apply.

8.1 Inclusion criteria

- Dermatology Department patients > 18 years undergoing surgical excision of ulcerated skin cancer of any type affecting any body site

8.2 Exclusion criteria

- Evidence of wound infection at the time of the procedure
- Skin tumour removal undertaken using curettage or Mohs micrographic surgery
- People without the capacity to consent for the study
- People who are on systemic immunosuppressive treatment
- People who are already taking oral antibiotics for any other reason

9 Recruitment, Screening and registration

9.1 Participant identification

Clinicians in the dermatology department will identify eligible participants at the time of initial consultation.

9.2 Screening logs

A screening log of all ineligible and eligible but not consented/not approached will be kept to inform any obstacles to enrolment in a future trial.

9.3 Recruitment rates

A total of 311 participants will be recruited at an expected rate of 39 per month. This is based on a previous audit in this centre which demonstrated that 55 people would have been eligible

for the study over a 3-week period. Assuming that just under half would agree to participate in the study, we anticipate recruiting 9 participants per week.

9.4 Informed consent

Where eligibility is indicated, patients will be provided with a brief explanation of the study by the clinical team. Assenting patients will be provided with a full verbal explanation of the study and Participant Information Leaflet (PIL) to consider by the clinical team. This will include detailed information about the rationale, design, and personal implications of the study. Following information provision, patients will be able to consider participation until the planned time of surgery and will be given the opportunity to discuss the study with their family and other healthcare professionals before they are asked whether they would be willing to take part in the study. Assenting patients will then be invited to provide informed, written consent. Assessment of eligibility and the informed consent process will be undertaken by a member of the clinical team, who are qualified by training and/or experience in taking informed consent to GCP standards or by a research support office/ nurse. The right of the patient to refuse consent without giving reasons will be respected. Further, the patient will remain free to withdraw from the study at any time without giving reasons and without prejudicing any further treatment. The participant's written informed consent must be obtained using the Participant Consent Form, which follows the Participant Information Leaflet. A record of the consent process detailing the date of consent and the version of the consent form used will be kept in the patient healthcare records. The original consent form will be retained in the Investigator Site File.

Please note, only when written informed consent has been obtained from the participant and they have been enrolled into the study can they be considered a study participant.

After the participant has entered the study, the investigator must remain free to give alternative treatment to that specified in the protocol, at any stage, if he/she feels it to be in the best interest of the participant. However, the reason for doing so should be recorded and the participant will remain within the study for the purpose of follow up and data analysis according to the treatment option to which he/she has been allocated. Similarly, the participant must remain free to withdraw at any time from the protocol treatment without giving reasons and without prejudicing his/her further treatment.

9.5 Registration

9.5.1 Registration

A record of the consent process detailing the date of consent will be kept in the patient healthcare records. To register a patient onto the OASIS study investigators or designee should complete the registration section of the Case Report Form (CRF). This will include:

- Site code
- Site name
- Participant full name
- Participant postal address or e-mail address
- Participant phone number
- Participant age
- Participant gender
- Date of consent of participant

10 Withdrawal & lost to follow-up

10.1 Withdrawal

Participants have the right to withdraw consent for participation in any aspect of the study at any time. The participants care will not be affected at any time by declining to participate or withdrawing from the study.

1. If a participant initially consents but subsequently withdraws from the study all their data will be removed. However participants cannot withdraw data after it has been anonymised for analysis.

10.2 Lost to follow up

1. Participants will be identified as lost to follow up if we are unable to contact them four weeks after their procedure.
2. Measures that we will take to try and get the missing information include three attempts to telephone or text the participants. If we are unable to contact the participant by telephone then and we will also send them a letter asking them to contact the study centre.'

11 Study procedures

The following are to be recorded before skin surgery on the CRF:

- Whether the participant has been recruited to the study previously
- Number of skin lesions being excised
- Number of skin lesions being excised that are ulcerated (if more than one ulcerated lesion, then the patient and researcher should agree on an index lesion for the OASIS study)
- Suspected type of index skin cancer (clinical diagnosis) – to be confirmed on histology
- Site of procedure(s)
- Size of index skin cancer (mm)
- Size of index tumoral ulceration

Participants and the clinicians performing the procedure will be asked whether they would agree for the participant to be randomised to no antibiotics, topical treatment eg. Inadine™ dressings, a short course of antibiotics or a longer course of antibiotics in a future RCT.

The following will be recorded after skin surgery on the CRF:

- Type of procedure
- Whether Inadine™ dressing applied to wound
- Whether topical antibiotics applied to wound
- Whether oral antibiotics prescribed

A questionnaire [Appendix 1] will be sent to participants by post or email at four weeks. A stamped-addressed envelope will be sent with the questionnaire for the reply if required.

11.1 Assessments

Assessment data required if participant develops suspected wound infection:

- Photograph of wound ('wound selfie'): the photos will be sent to the CTR to determine whether this is a feasible method of assessing wounds, however the photos will not be analysed.

Figure 1. Schedule of enrolment, interventions and assessments¹

Procedures	Visits (insert visit numbers as appropriate)			
	Screening	Baseline	(If concern about SSI)	(Follow Up)
Eligibility assessment	X			
Informed consent		X		

¹ Taken from the HRA CTIMP protocol template (2016).

Demographics		X		
Clinician / Participant agreement for future RCT		X		
Procedure data		X		
Skin swab (only CAVUHB participants)		X		
Wound photograph			X	
Questionnaire				X

11.2 Follow-up

Final data will be collected by questionnaire four weeks after the procedure. Any further follow-up appointments in the clinic will be based on clinical discretion and no further appointments will occur specifically for the study.

11.3 Skin swabs (CAVUHB participants only)

Participants enrolled to the study at the University Hospital of Wales, Cardiff will have swabs of ulcerated skin tumours taken and analysed in the Public Health Wales laboratory at the University Hospital of Wales, Cardiff.

It is the responsibility of the study site to ensure that samples are appropriately labelled in accordance with the study procedures to comply with the current Data Protection legislation. Biological samples collected from participants as part of this study will be transported, stored, accessed and processed in accordance with national legislation relating to the use and storage of human tissue for research purposes and such activities shall at least meet the requirements as set out in the 2004 Human Tissue Act.

Swabs of the ulcerated tumours will be taken with no prior cleaning prior to skin surgery. Completed swabs will be deposited in specimen collection baskets within the dermatology department and will be shipped to the laboratory via the standard portering system.

Swabs will be cultured onto a range of non-selective and selective media. Bacterial pathogens will be semi-quantified and identified using MALDI-ToF and other tests where applicable. Microbiological infection will be determined according to local Standard Operating procedures,

based upon UK national Standards in Microbiology Investigations (SMI) guidelines. After the skin swabs have been processed then they will be destroyed according to laboratory regulations.

The aim of this is to identify the most common organisms that grow in ulcerated tumours which will help to guide antibiotic choice in a future randomised controlled trial.

Currently, there is no consensus on which antibiotic would be most appropriate to reduce the risk of surgical site infection in ulcerated skin tumours. This may be partly explained by the paucity of data regarding pathogens of ulcerated skin tumours. One single-centre study in Australia isolated *Staphylococcus aureus* in 93 of 97 ulcerated lesions and gram-negative bacteria (including *Klebsiella*, *Acinetobacter*, *Proteus*, *Serratia* and *Escherichia* species) in 7 of 97 ulcerated lesions.¹⁶ However, it is not clear whether this was conducted in a research laboratory setting or in a clinical setting where the laboratory would aim to identify the presence of known skin pathogens.

12 Statistical considerations

12.1 Sample size

Given the wide range in reported SSI from published case series between 2-33%, we anticipate a SSI of approximately 10% in our participants with ulcerated skin tumours. Our aim is to recruit 311 participants with an intended sample size of 283 participants (allowing for a dropout rate of 10%). This will give a 95%CI of between 6.9% to 13.5%.

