List summary of protocol amendments here whenever a new version of the protocol is produced. Ensure details are also updated in a full protocol change log.

[figure not shown]
2 Synopsis

Short title	Observational study to investigate Surgical site Infection in ulcerated Skin cancers
Acronym	OASIS
Internal ref. no.	
Clinical phase	N/A
Funder and ref.	UK Dermatology Clinical Trials Network (UK DCTN) Dermatology Forum for Wales CAVUHB Dermatology Department Research Funds
Study design	Observational prospective study
Study participants	People undergoing surgical excision of ulcerated skin cancer of any type at any body site in the dermatology departments at the University Hospital of Wales Cardiff; Churchill Hospital, Oxford and Queen Elizabeth Hospital, Birmingham.
Planned sample size	311
Inclusion criteria	> 18 years old
Exclusion criteria	
 1) Evidence of wound infection at the time of the procedure 2) Skin tumour removal undertaken curettage or Mohs micrographic surgery 3) People without the capacity to consent for the study 4) People who are on systemic immunosuppressive treatment 5) People who are already taking oral antibiotics
Treatment duration	N/A

Follow-up duration	4 weeks
Planned study period	8 months (recruitment phase) + 1 month (follow-up phase) + 5 months (analysis and write up phase)
Primary objective	To ascertain the proportion of surgical site infections following excision of ulcerated skin tumours in Dermatology Departments.
Secondary objectives	Feasibility work to inform the design of a future randomised controlled trial to investigate whether the use of peri-operative antibiotics in ulcerated skin tumours reduces the proportion of patients with surgical site infection.
Primary outcomes	Proportion of participants with surgical site infection (SSI) identified by postal questionnaire four weeks after surgery.

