12.4 Inclusion in analysis

All screened patients will be reported. For each analysis, only patients with relevant evaluable data will be analysed. Where relevant, differences between those with and without the relevant evaluable data will be reported as a check for bias.

13 Analysis

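### Section 12.1 is internally inconsistent: 311 recruited with 10% dropout leaves about 280 evaluable participants, not 283 (minor; a one-sentence correction)

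*Combined protocol and SAP*

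**What the plan says.** Section 12.1 gives the recruitment target, the evaluable number and the dropout allowance in one sentence: "Our aim is to recruit 311 participants with an intended sample size of 283 participants (allowing for a dropout rate of 10"%). The planning value for the primary outcome comes just before it: "we anticipate a SSI of approximately 10% in our participants with ulcerated skin tumours". The precision claim follows: "This will give a 95%CI of between 6.9% to 13.5"%. No formula is shown for the step between 283 and 311, no source is given for the 10% dropout, and no target half-width is stated.

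The figure of 311 appears elsewhere as the fixed target. The synopsis has "Planned sample size 311", the lay summary in section 3.2 repeats it, and section 9.3 says "A total of 311 participants will be recruited at an expected rate of 39 per month". None of these places mentions 283 or dropout.

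Three other sections bear on what dropout means here. Section 10.1 removes the data of participants who withdraw, unless the data have already been anonymised for analysis. Section 10.2 defines loss to follow-up as failure to make contact four weeks after the procedure. Section 12.4 sets the analysis population: "For each analysis, only patients with relevant evaluable data will be analysed".

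**The concern.** Withdrawal and loss to follow-up, as sections 10.1 and 10.2 describe them, happen to people already enrolled. Section 12.4 then analyses only those with evaluable data. The evaluable number should therefore be the number recruited times one minus the dropout proportion. With the plan's own 311 and 10%, that product is not 283.

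The primary aim is to estimate one proportion, and section 4 says that proportion is needed to size a future randomised trial. The expected precision is the only justification offered for the sample size, and it follows directly on the figure of 283. If the recruitment target and the dropout allowance do not deliver 283, the stated basis of the sample size is not met on the plan's own assumptions. What needs settling is whether this is more than rounding, and whether it changes the precision.

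**Working it through.** Inputs, all from section 12.1: recruited N = 311; intended evaluable n = 283; dropout d = 10%; anticipated proportion p = 10%; printed 95% interval 6.9% to 13.5%.

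**Step 1. Reproduce the plan's 311.**
- Evaluable number plus 10% of itself: n x (1 + d) = 283 x 1.1 = 311.3, which rounds to the nearest whole number as 311.
- Inflation for a 10% loss among those recruited: n / (1 - d) = 283 / 0.9 = 314.4, so 315.

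Of these two usual calculations, only the first gives 311.

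**Step 2. Apply the stated dropout to the stated target.**
- N x (1 - d) = 311 x 0.9 = 279.9, about 280 evaluable.
- Shortfall against the stated figure: 283 - 280 = 3, and 3/283 = 1.1%.
- Shortfall at recruitment if 283 is kept with 10%: 315 - 311 = 4, and 4/311 = 1.3%.
- Dropout implied by 311 and 283: (311 - 283)/311 = 28/311 = 9.0%.

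This is not rounding: 279.9 does not round to 283, and 314.4 does not round to 311.

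**Step 3. Effect on precision.** Normal-approximation half-width = 1.96 x sqrt(p(1 - p)/n) at p = 0.10.

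| Evaluable n | Half-width (points) | 95% interval |
|---|---|---|
| 283 | 3.495 | 6.50% to 13.50% |
| 280 | 3.514 | 6.49% to 13.51% |

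The half-widths differ by about 0.02 points. To one decimal both intervals are 6.5% to 13.5%.

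**Step 4. Does the slip account for the printed 6.9% to 13.5%?** The nearest whole-number counts to 10% are 28 of 283 (9.9%) and 28 of 280 (10.0%).

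| Method | 28/283 | 28/280 |
|---|---|---|
| Normal approximation | 6.42% to 13.37% | 6.49% to 13.51% |
| Wilson | 6.93% to 13.93% | 7.01% to 14.07% |
| Clopper-Pearson | 6.68% to 13.98% | 6.75% to 14.13% |
| Agresti-Coull | 6.89% to 13.97% | 6.97% to 14.11% |
| Jeffreys | 6.82% to 13.78% | 6.90% to 13.92% |

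No row matches both printed limits at either number, so replacing 283 with 280 does not repair the interval.

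**The case against.** The strongest reply is that nothing turns on this. The study estimates a single proportion, with no hypothesis test, power requirement or stated precision threshold, and the interval to one decimal is the same with 280 as with 283. The 10% dropout is itself an unsourced planning figure. Each percentage point of dropout is worth 311 x 0.01 = 3.1 participants, so the discrepancy equals about one point in an uncertain response rate. Section 10.2 also plans telephone or text attempts and a letter for non-responders. All of this stands and sets the priority low. It does not make the three figures agree, and neither does the provision in section 12.2 for imputing missing data if they become a problem, since that is not offered as the basis for 283.

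Four stronger readings are tempting, and the documents support none of them.

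- A reader might take multiplication by 1.1 as the established cause. It fits, but section 12.1 shows no formula. A planned loss of 9% described loosely as 10% would produce the same sentence, and rounding 311.3 up would give 312.
- A reader might conclude that a precision target is missed. A half-width of 3.5 points at 10% needs 1.96^2 x 0.09 / 0.035^2 = 282.2, hence 283, and it fits the printed upper limit. But the protocol never states that target, so 280 cannot be said to fail it.
- A reader might suppose that the slip explains the printed interval. Step 4 shows that it does not. One combination in the wider check, 31 of 315 by Jeffreys, gives 6.92% to 13.50%. However, 315 appears nowhere in the protocol and would be a number recruited, not evaluable. Section 13.1 names only Wilson's method, and only for proportions below 5%.
- A reader might count section 9.3 as a second instance. It only repeats 311, which agrees with 39 per month over the eight-month recruitment phase (39 x 8 = 312).

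**Conclusion.** The inconsistency is real and minor. On the plan's own figures, 311 recruited with 10% dropout yields about 280 evaluable participants, 3 (1.1%) fewer than the stated 283; equivalently, 311 and 283 imply 9.0% dropout. The normal-approximation half-width at 10% changes from 3.50 to 3.51 points. The primary estimate is not threatened, and no case for recruiting more people follows.

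The conclusion assumes that dropout is a proportion of those recruited, which is how sections 10.1, 10.2 and 12.4 read together. The precision comparison also assumes a true proportion of 10% and the normal approximation. The explanation by a factor of 1.1 remains an inference, and the mismatch does not depend on it. The printed interval of 6.9% to 13.5% is a separate question that this point neither causes nor resolves. Severity: low.

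**What to change.** Amend one sentence in section 12.1, in either of two ways:

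- State that 311 recruited with 10% dropout gives about 280 evaluable participants, and compute the precision statement for 280. By the normal approximation at 10%, that is 6.5% to 13.5%.
- Keep 283 as the evaluable number and state the dropout allowance as 9%.

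Either way, show the calculation and name the interval method so that a reader can reproduce the figures. The recruitment target stays at 311, so the synopsis, the lay summary and section 9.3 need no change. The cost is one reworded sentence; under the first option the plan also quotes a slightly smaller evaluable number. Design, conduct and recruitment are unaffected.

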13.1 Main analysis

All analyses will report a proportion and 95% confidence interval. Where appropriate (i.e., if the proportion is <5%), the 95% confidence interval will be reported as per Wilson's method.

17

14 Data Management

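### Section 12.1: the expected 95% CI of 6.9% to 13.5% does not follow from 283 participants at 10% by any of the methods checked; the normal approximation gives 6.5% to 13.5%

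*Combined protocol and SAP*

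**What the plan says.** Section 12.1 (Sample size) links three statements.

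- Anticipated proportion: "we anticipate a SSI of approximately 10% in our participants with ulcerated skin tumours".
- Numbers: "Our aim is to recruit 311 participants with an intended sample size of 283 participants (allowing for a dropout rate of 10" per cent).
- Resulting precision: "This will give a 95%CI of between 6.9% to 13.5" per cent.

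Section 12.1 does not say how the interval was calculated. Section 13.1 (Main analysis) says every analysis will report a proportion with a 95% confidence interval. It names Wilson's method only for small proportions: "if the proportion is <5%), the 95% confidence interval will be reported as per Wilson's method". At the anticipated 10%, therefore, neither section states a method.

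**The concern.** The printed interval is not symmetric about 10%: it extends 3.1 points below and 3.5 points above, and its midpoint is 10.2%. It therefore cannot be a Wald interval around 10%. It is also narrower than expected from 283 participants.

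The study estimates one proportion, with no comparison and no hypothesis test, so this interval is the whole case for the sample size. Section 4 says the estimate is needed to size a later randomised trial. A reader should be able to reproduce the only precision statement in the plan, and it should not claim more precision than the planned number gives.

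**Working it through.** **Inputs** (all from 12.1): p = 0.10; intended n = 283; recruited 311; dropout 10%; 95% two-sided, z = 1.96.

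**1. Where 283 comes from.** For a half-width d under the normal approximation, n = z² p(1 − p) / d². With d = 0.035: 1.96² × 0.1 × 0.9 / 0.035² = 282.2, rounded up to 283. This reproduces the plan's sample size.

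**2. The interval that goes with it.** Half-width = 1.96 × √(0.1 × 0.9 / 283) = 0.03495. The limits are 10% ± 3.495 points, that is 6.505% to 13.495%, or 6.5% to 13.5%. The upper limit agrees with the plan; the lower limit (6.9%) does not.

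**3. Other methods at 10%, n = 283.**

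| Method | Lower % | Upper % |
|---|---|---|
| Printed in 12.1 | 6.9 | 13.5 |
| Wald | 6.50 | 13.50 |
| Wald, continuity-corrected | 6.33 | 13.67 |
| Wilson | 7.02 | 14.05 |
| Wilson, continuity-corrected | 6.88 | 14.25 |
| Agresti-Coull | 6.98 | 14.09 |
| Exact (Clopper-Pearson) | 6.76 | 14.10 |
| Jeffreys | 6.91 | 13.90 |
| Uniform prior | 7.03 | 14.05 |
| Logit | 7.01 | 14.08 |
| Arcsine | 6.78 | 13.76 |
| Mid-P (28/283) | 6.81 | 13.80 |

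None gives the printed pair. The widths run from 6.97 (arcsine) to 7.37 (continuity-corrected Wilson), with Wald at 6.99; the printed width is 13.5 − 6.9 = 6.6.

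Whole-number counts do not help. At 28/283 Wald gives 6.4 to 13.4 and Wilson 6.9 to 13.9; at 29/283 Wald gives 6.7 to 13.8 and Wilson 7.2 to 14.3.

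**4. Other sample sizes.** At n = 280 and 10%: Wald 6.49 to 13.51, Wilson 7.01 to 14.07, Jeffreys 6.90 to 13.92, exact 6.75 to 14.13. In a search over sample sizes and whole-number counts, the pair 6.9 and 13.5 first appears at n = 306 (Jeffreys, 30/306). Later matches include Wilson at 30/309 and arcsine at 31/311. Keeping 306 of 311 means dropout of 5/311 = 1.6%, against the 10% allowed.

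**5. Sample size needed for the printed width.** At 10%, a width of 6.6 points or less needs 317 (arcsine), 318 (Wald or Jeffreys), 321 (Wilson) or 347 (exact). Both printed limits are rounded, so the true width could be up to 6.7; the numbers then fall to 307 (arcsine), 308 (Jeffreys), 309 (Wald), 311 (Wilson) and 337 (exact). All are well above 283.

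**6. Dropout in the same sentence.** 311 × 0.90 = 279.9, so 10% dropout leaves 280. The 311 appears to be 283 × 1.10 = 311.3. Keeping 283 of 311 is a dropout of 1 − 283/311 = 9.0%. To one decimal, Wald at 280 is still 6.5% to 13.5%.

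**The case against.** The strongest objection is about weight. Nothing in the design depends on a precision threshold, the discrepancy is about 0.4 points on one limit, and neither recruitment nor the interval eventually reported would change. It is probably a typing slip. That is fair as to size, but it does not make the printed figure correct.

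The second objection is that the normal approximation is not proven to be the intended method. A slip in the upper limit would also fit: Jeffreys at 10% and Wilson at 28/283 both give 6.9% to 13.9%, and Wilson is the only interval method the plan names. This stands as a caution. Against it, 283 matches a 3.5-point Wald half-width, and 13.1 keeps Wilson for proportions below 5%. Wald is the more likely source, but only the authors can settle it.

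The third is that the anticipated proportion is only approximate. That does not rescue the figure: letting the proportion vary from 8.5% to 11.5% at n = 283 or 280 does not recover the printed pair.

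Finally, 280 is not the only repair for the dropout mismatch. The authors could keep 283 and state 9% dropout instead.

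**Conclusion.** The concern holds. With 283 participants and a proportion of 10%, no method checked gives 6.9% to 13.5%, and the same is true at 280. At either number the printed interval is narrower than every method checked gives. If Wald was intended, the lower limit should read 6.5% and is 0.4 points too high; if Jeffreys was intended, or Wilson at 28/283, the upper limit is 0.4 points too low.

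That the interval cannot be reproduced rests only on the figures in 12.1 and the list of methods tried. The specific correction to 6.5% rests on inferring the normal approximation from the 283. The dropout mismatch (280 against 283) is minor and does not move the Wald limits to one decimal. The point is worth correcting, but it does not threaten the study.

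**What to change.** In 12.1, replace the numbers and precision statement with, for example:

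> Recruiting 311 and allowing for 10% dropout gives about 280 evaluable participants; at an SSI proportion of 10% the 95% CI (normal approximation) is 6.5% to 13.5%.

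If 283 is to be kept as the evaluable number, state the dropout as 9%; the interval is the same. If another method was intended, name it and give its limits, for example Wilson, 7.0% to 14.0% at 10% and n = 283.

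In 13.1, name the method for proportions of 5% or more so that it matches 12.1.

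The cost is one sentence in 12.1 and a few words in 13.1. The stated precision becomes about 0.4 points wider, and no extra recruitment is needed.
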